Study Product, Dose, Route, Regimen	Health coach face-to-face visits, with follow-up telephone calls, self-management support, and primary care provider feedback
FDA status of product	not applicable

Duration of administration	6-month intervention; 6-month maintenance evaluation (12-month total follow-up)
Reference therapy	Usual Clinical Care
Statistical Methodology	The primary comparisons for the co-primary outcomes of systolic and diastolic blood pressure change from baseline to 6 months will be done using analysis of covariance with MyHEART and baseline blood pressure as independent covariates. The primary comparisons for the secondary outcome of hypertension control will be based on Fisher's exact tests. Mediation analysis will be performed for Aim 3.

Schematic of Study Design

Figure: Eligibility, Enrollment, Randomization, Follow-up and Analysis

Contents

Study Summary.....	6
1 Key Roles.....	12
2 Background and Introduction.....	12
2.1 Background and Rationale.....	13
2.1.1 Development of MyHEART.....	13
2.2 Hypothesis.....	14
2.3 Study Agent.....	14
2.4 Summary of Clinical Data.....	15
2.5 Potential Risk and Benefits to Subjects.....	16
2.5.1 Known Potential Risks	16
2.5.2 Alternative to Study Participation	17
2.5.3 Protection Against Risks	17
2.5.4 Adverse Event Reporting	19
2.5.5 Potential Benefits to the Subjects	20
2.5.6 Risk Minimization	20
3 Study Design and Endpoints.....	21
3.1 General Design	21
3.1.1 Primary Study Endpoints.....	22
3.1.2 Secondary Study Endpoints.....	22
3.1.3 Primary Safety Endpoints.....	22
4 Study Subjects – Enrollment and Withdrawal.....	22
4.1 Subject Population	22
4.2 Inclusion Criteria.....	23
4.3 Exclusion Criteria	23
4.4 Subject Screening for Recruitment	24
4.4.1 Subject Identification	24
4.4.2 Recruitment and Retention Strategies	24
4.5 Vulnerable Populations	25
4.5.1 Subject Capacity	25
4.5.2 Subject/Representative Comprehension	25
4.6 Informed Consent.....	26
4.6.1 Process of Consent.....	26
4.6.2 Consent Form.....	26
4.6.3 HIPAA.....	26
4.6.4 Revoking Consent.....	27
4.6.5 Costs to the Subject	27
4.6.6 Payment for Participation	27
4.7 Early Withdrawal of Subjects	27

4.7.1	Premature termination of study	27
4.7.2	When and How to Withdraw Subjects.....	28
4.7.3	Data Collection and Follow-up for Withdrawn Subjects.....	28
5	Study Procedures	28
5.1	Prior and Concomitant Therapy	28
5.2	Randomization and Blinding of Intervention	28
5.3	Established Standard of Care	29
5.4	Study Visits.....	29

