3.1.1 Primary Study Endpoints

The co-primary clinical outcome is a significant, clinically important change in systolic and diastolic blood pressure at 6 and 12 months.^{21,36} The 6-month outcome assesses the end of the 6-month MyHEART intervention.⁴³ The 12-month outcome (*i.e.*, 6 months post-intervention)⁵⁸ assesses maintenance of blood pressure and sustainability of behavior change after study completion. In contrast to the baseline assessment, follow-up questionnaires and physiologic measurements will be conducted, obtained, and documented during the first visit of the 6- and 12-month visits to decrease missing data.

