If a potentially eligible young adult already completed 24-hour ambulatory blood pressure monitoring through their UW Health or Aurora Health Care Clinic within the past 3 months, they do not need to repeat 24-hour ambulatory blood pressure monitoring for study eligibility. The ambulatory blood pressure monitoring report will be reviewed in their electronic health record to evaluate for white coat hypertension (an exclusion criteria). If eligible, the participant will be able to proceed with the Screening Visit 2/Baseline Assessment Visit. The individual's honorarium for Visit 1 and Visit 2 will not be adjusted/decreased.

Screening Visit 2/Baseline Assessment Visit: After receiving a 24-hour AMBp monitor, participants will be asked to return for Visit 2 on the next business day. Participants will have up to 30 days from Screening Visit 1 to return for Visit 2 without having to restart with the telephone screening process. A research staff member (not the individual acquiring consent or enrolling during this visit) will evaluate the mean 24-hour ambulatory blood pressure. If there is white coat hypertension, the patient is ineligible, and will receive an incidental finding letter to share with their primary care provider. Remaining eligible patients will be enrolled, randomized to MyHEART or usual care, and complete the baseline assessment.

5.4.1.2 Baseline/Follow-Up Data Collection:

All research staff will be trained in all key elements of the protocol and use of the data management system.

Anthropometric Measurements

- **Height** will be determined at each assessment visit using a wall-mounted stadiometer, without shoes or other outdoor footwear. Two measures of height will be taken and the average of the two will be used. We will repeat the measurement of height at each assessment visit because growth may still be occurring in young adults. Height will be measured to the nearest 0.1 cm.
- **Weight** will be determined at each assessment in light indoor clothes, removing all excess layers of clothing, and without shoes at all visits. All scales will be calibrated using standard weights, annually by the Bureau of Weights and Standards and quarterly by trained study personnel. Weight will be measured to the nearest 0.1 kg.
- **Body mass index (BMI)**. The weight and height measures will be used to calculate Body Mass Index (weight in kilograms divided by height in meters squared; kg/m²)

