Blood pressures at each research site will be assessed with a Dinamap Monitor. Cuff size will be determined by arm circumference. An appropriate sized¹⁶⁶ blood pressure cuff will be connected to an automated sphygmomanometer (Dinamap). Each site will have the following cuff sizes available: small adult (for arm circumference of 22-26 cm), regular adult (27-34 cm), and large adult (35-42 cm). A blood pressure measurement will be obtained on the right upper arm, then the left upper arm, for the initial assessment. Right arm blood pressures will be subsequently used for the initial and follow-up visits, unless the left arm systolic blood pressure is ≥10 mmHg higher. The average of the second and third systolic and diastolic pressures, each taken 1 minute apart, will define the baseline clinic blood pressure.¹⁶⁷ If a participant's upper arm is too large, a forearm blood pressure will be obtained. All participants (intervention and control) will receive copies of their baseline, 6-month, and 12-month research clinic blood pressures to share with their usual healthcare provider, and will receive instructions on recommended primary care clinic follow-up.^{43,168}

24-Hour Blood Pressure Monitoring:¹⁶⁹⁻¹⁷¹ 24-hour blood pressure monitoring will take place at baseline, 6 months, and 12 months. Staff trained in the use of the 24-hour ambulatory blood pressure monitor will apply the appropriate sized cuff to the subjects' non-dominant arms unless the systolic blood pressure difference as measured during the clinic blood pressure assessment is >10 mmHg, in which case the arm with the highest value obtained

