All intervention participants will start with the home blood pressure monitoring module. The first follow-up phone call will address hypertension knowledge and review home blood pressure monitoring. Home blood pressure monitoring education will also be provided during all follow-up phone calls. The order of the remaining modules will be guided by participant's choice and tailored to their goals.^{170,171} Fewer modules than calls allows some topics to be repeated as

needed and per the participants' requests. Current tobacco users will be referred to the Wisconsin Tobacco Quit Line (<http://www.ctri.wisc.edu/quitline.html>) when ready to attempt cessation and their primary care provider will be notified of their intention to quit via the EHR. The participant will be encouraged to also discuss alcohol reduction/cessation with their primary care provider if they report consuming >14 alcohol beverages/week.¹²² The MyHEART team created handouts to include specific topics requested by our young adult focus groups (see Appendix). The MyHEART handouts were formatted with a Flesch-Kincaid readability of ≤6th grade.¹⁷²

5.4.3 Follow up:

Table. Acceptable Window for Study Visits (including weekends)

Visit	Window	Activities
Baseline (Visit 1)	No more than 30 days from telephone screening phone call	Written, informed consent, clinic blood pressure, 24-hour AMBP placement, provide participant remuneration
Baseline (Visit 2)	No sooner than 24 hours after Visit 1 and no more than 21 days after Visit 1	Clinic blood pressure, 24-hour AMBP removal, if eligible, enrollment, randomization, baseline screening questions and assessment, provide participant remuneration
6-month (Visit 3)	No later than 30 days since the last health coach call (intervention arm) or the scheduler call (routine/usual care)	Clinic blood pressure, 24-hour AMBP placement, 6-month follow-up assessment (ex: BMI), questionnaires, provide participant remuneration
6-month (Visit 4)	No sooner than 24 hours from Visit 3 and no more than 21 days from Visit 3	24-hour AMBP removal, provide participant remuneration
12-month (Visit 5)	No later than 30 days since scheduler call (both intervention and usual care arm)	Clinic blood pressure, 24-hour AMBP placement, 6-month follow-up assessment (ex: BMI), questionnaires, provide participant remuneration
12-month (Visit 6)	No sooner than 24 hours from Visit 5 and no more than 21 days from Visit 5	24-hour AMBP removal, provide participant remuneration

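### Baseline questionnaires are placed after randomisation, and baseline clinic pressure is not tied to either of the two visits at which it is measured

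*Combined protocol and SAP*

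**What the plan says.** Section 5.4.1.1 describes Visit 2, once white coat hypertension has been excluded: "Remaining eligible patients will be enrolled, randomized to MyHEART or usual care, and complete the baseline assessment". The visit table in section 5.4.3 gives the same order for the questionnaires. Its Visit 2 row reads "Clinic blood pressure, 24-hour AMBP removal, if eligible, enrollment, randomization, baseline screening questions and assessment, provide participant remuneration". Its Visit 1 row, also labelled as baseline, reads "Written, informed consent, clinic blood pressure, 24-hour AMBP placement, provide participant remuneration". Clinic pressure is thus measured at two visits.

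Section 5.4.1.2 defines the baseline clinic value from one set of readings: "The average of the second and third systolic and diastolic pressures, each taken 1 minute apart, will define the baseline clinic blood pressure". No visit is named. The Study Summary gives the primary analysis as "analysis of covariance with MyHEART and baseline blood pressure as independent covariates" and does not say whether that pressure is clinic or ambulatory. Section 2.2 covers both, and section 5.2 treats ambulatory monitoring as the gold standard.

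**The concern.** A baseline should be fixed before anyone knows the arm. A participant who has just been told the allocation, and in the intervention arm may already have been trained on a home monitor, can answer questions on activity, diet, competence or motivation differently. The comparison of change from baseline then carries part of that reaction as if it were treatment effect, or has treatment effect hidden by it.

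For clinic pressure the issue is definition. With two eligible sets of readings and no rule, two analysts can derive different baselines from the same data, and the text does not state outright that the chosen reading precedes allocation.

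**Working it through.** **Order at Visit 2**

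1. Section 5.4.1.1: enrolment, randomisation, baseline assessment.
2. Table in section 5.4.3: clinic pressure, monitor removal, eligibility, enrolment, randomisation, baseline questions and assessment.
3. Section 5.2: the assessor conducting Visit 2 telephones for the allocation, so that assessor knows the arm from then on. The same section promises blinding for the 6- and 12-month assessors only. Section 2.5.6 makes a wider claim of staff blinding that does not fit with the call.
4. Section 5.4.1.2: intervention participants are trained on the home monitor at the enrolment visit, so they know their arm.

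The two sources agree that the questionnaires follow randomisation. For clinic pressure, the table puts the reading before it. Section 5.4.1.1 says nothing specific, but pressure is described under the data-collection heading that covers baseline, so a reader could count it as part of the baseline assessment.

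The exposed outcomes include the Godin questionnaire and ASA24 (section 5.4.1.2) and change in the PCS, HCCQ and TSRQ scores (section 3.1.2). Section 6.2 analyses Aim 2 differences from baseline to 6 months by t-tests or Wilcoxon tests and by ANCOVA. If knowing the arm shifts one arm's mean baseline score by s, the unadjusted difference in mean change moves by s. The ANCOVA difference moves by b × s, where b is the slope of the 6-month value on baseline. The documents give neither s nor b, so no size can be attached. The available yardstick is the Aim 2 target in section 6.1, about 0.4 SD of the differences.

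**Which visit supplies clinic baseline**

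The hints conflict. Section 3.1.1 points to Visit 2: "In contrast to the baseline assessment, follow-up questionnaires and physiologic measurements will be conducted, obtained, and documented during the first visit". Section 5.4.1.2 points to Visit 1: "A blood pressure measurement will be obtained on the right upper arm, then the left upper arm, for the initial assessment", since the between-arm check is a Visit 1 procedure (sections 2.5.1 and 5.4.1.1). The visits may be up to 21 days apart in the table but up to 30 in section 5.4.1.1.

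**The plan's power figure**

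Inputs from section 6.1: effects 6.3 and 4.0 mmHg, SDs 13.6 and 9.7, effective N 264 (132 per arm), two-sided 0.025 each (critical value 2.241). Power = Φ(effect / (SD × √(2/132)) − 2.241).

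- Systolic: 6.3 / 1.674 = 3.763; Φ(1.522) = 0.936, against 0.94 stated.
- Diastolic: 4.0 / 1.194 = 3.350; Φ(1.109) = 0.866, against 0.87 stated.

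Both reproduce without any covariate adjustment.

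**Gain from averaging two visits**

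Let r be the correlation between Visits 1 and 2, and ρ the correlation of either visit with 6 months. Neither is in the documents; r = 0.5-0.7 and ρ = 0.4-0.6 are assumed, with equal variances and the same ρ for both visits. Residual variance is proportional to 1 − ρ² with one visit. The two-visit mean has correlation ρ√(2/(1+r)) with 6 months, giving 1 − 2ρ²/(1+r).

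| r | ρ | One visit | Two-visit mean | Ratio | Reduction |
|---|---|---|---|---|---|
| 0.6 | 0.5 | 0.750 | 0.6875 | 0.917 | 8% |
| 0.5 | 0.6 | 0.640 | 0.520 | 0.813 | 19% |
| 0.7 | 0.4 | 0.840 | 0.812 | 0.966 | 3% |

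The central case equals about 9% more patients (1/0.917 = 1.09). The 19% corner needs ρ above r, which is unlikely when the baseline visits are weeks apart and follow-up is at 6 months. At r = ρ = 0.6 the ratio is 0.550/0.640 = 0.859, a 14% reduction.

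**Does power depend on it?**

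Read the stated SDs as SDs of change, with a common correlation ρ between all visits. The single-visit residual variance is then SD² × (1+ρ)/2. At ρ = 0.5 the systolic residual SD is 13.6 × √0.75 = 11.78. For ρ of 0.3, 0.5 and 0.7:

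- One visit: power 0.992, 0.982, 0.967 systolic; 0.972, 0.948, 0.918 diastolic.
- Two-visit mean: 0.995, 0.991, 0.987 systolic; 0.979, 0.969, 0.960 diastolic.

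Every single-visit value exceeds the stated power.

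**The case against.** A reader might infer that the covariate of the primary analysis is measured after allocation and that the primary estimate is therefore biased. On purely assumed figures, a shift of 1-3 mmHg in one arm and a slope of 0.3-0.7 would move the systolic estimate by 0.3 to 2.1 mmHg (1 × 0.3 to 3 × 0.7), against a design effect of 6.3. The documents do not support that reading. Visit 1 pressure necessarily precedes allocation, and the table lists the Visit 2 reading before eligibility and randomisation. The covariate may also be ambulatory, in which case the 24-hour mean is evaluated for eligibility before randomisation. The clinic device is automated, which limits examiner influence.

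It can also be said that these are lists of activities rather than sequence rules, that section 5.2 has REDCap check data completeness before randomisation, and that the full SAP and study calendar sit in appendices outside the text reviewed here and may settle the definitions. One pre-specified visit would also be a valid baseline.

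Most of this stands for blood pressure. It does not answer the questionnaire point: the prose and the table both put the assessment after randomisation, and section 5.2 does not say which data must be complete. An appendix definition would still leave section 5.4.1.1 to be brought into line.

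**Conclusion.** The order of the baseline questionnaires is a real weakness for the unblinded self-reported outcomes of Aims 2 and 3. Its size cannot be estimated from the documents. It touches secondary outcomes and an aim that section 6.1 calls exploratory.

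For clinic pressure, the visit is undefined and pre-allocation measurement is suggested but not secured. Clinic or ambulatory is also left open for the primary covariate. Bias in the primary result is not shown.

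Averaging the two visits is a precision gain only: 3-19% lower residual variance, resting on the assumed correlations and equal variances. A reader might infer that a single-visit baseline costs the trial its planned power. It does not, because the stated 0.94 and 0.87 are obtained with no covariate at all.

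**What to change.** 1. Reorder section 5.4.1.1 and the Visit 2 row of the table so that all baseline assessments and clinic pressures are recorded in REDCap before the randomisation call. Reconcile the 21- and 30-day limits for Visit 2 at the same time.
2. State whether the primary ANCOVA covariate is clinic or ambulatory pressure. Where clinic pressure is analysed, define baseline as the mean of the Visit 1 and Visit 2 values, each the mean of readings 2 and 3.

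No new measurement is needed. The cost is amended wording, a changed visit order at both sites, and baseline assessments completed before allocation is known, which is a small burden because eligibility can be settled first.

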5.4.2 Intervention

Health Coach Training: Health coaches will receive training that builds on their prior education in motivational interviewing¹⁷⁹ and hypertension management, using self-determination theory concepts. Training intensity is based on prior studies¹²⁷ and resources from our pilot: interactive didactic lectures, videos,¹⁸⁰ and the MyHEART health coach guide (see Appendix). Trainers will observe health coaches with role-playing, followed by problem solving and debriefing.¹⁸¹⁻¹⁸³ Health coaches will already be certified as an exercise physiologist (American College of Sports Medicine certification), registered dietitian (Academy of Nutrition and Dietetics) with at least 3 years of clinical experience including chronic disease management and adult education/counseling, or a registered nurse. Health coaches will receive training on the MyHEART coaching guide that builds on their prior education in motivational interviewing and hypertension management, using self-determination theory concepts. Training will include interactive didactic lectures and videos and the MyHEART health coach guide. The trainer will also observe health coaches with role playing followed by problem solving and debriefing. The references (scientific articles, etc.) that will be given to the coach are optional reading materials for them to select based upon additional questions or training needs about motivational interviewing, self-determination theory, and/or blood pressure lowering. The individual needs of each coach will be identified during training and they will be directed to appropriate references. All subject handouts developed for this study will be reviewed during training with discussion on when and how to include the handouts to reinforce the telephone calls. Handouts will be distributed after each phone call either by postal mail or email (based upon subject's preference).

Health Coach Fidelity: An audio recorder will be placed on the table during the health coach calls. The goal is to record the coach's comments and adherence to the curriculum and protocol, and use of the self-determination theory. The participant's first name will be heard on the audio recording as he/she communicates with the participant. A recording device will NOT be attached to the phone or phone line. The secure storage and transmission of these audio files is summarized in the "Protection Against Risks" section.

Health Coach Phone Calls: Intervention arm participants will receive a health coach phone call every 2 weeks for 6 months, for a total of 12 calls. The first call will be scheduled at the screening visit and subsequent calls will be set up at the end of each prior call. If a participant is unavailable, the health coach will leave a message and reschedule the call up to 3 times. Once a coach is ready to make calls for the MyHEART intervention: during each call, the health

coaches will review and discuss home blood pressures, if available, from home blood pressure monitoring, and address barriers and concerns to home blood pressure monitoring. The MyHEART coaches will also recommend clinic follow-up based on the 2-week average home blood pressures – see coach's guide, which coincides with UW Health's blood pressure follow-up recommendation. During each telephone call, the coach will guide the subject on selecting health behavior goals and completing the goal sheet (uploaded in this application). In addition to home blood pressure monitoring, subjects will be able to choose which topics from the 8 additional hypertension education modules they want to address during a call (options include: hypertension knowledge, low sodium, DASH eating plan, weight loss/maintenance, smoking cessation, moderate alcohol consumption, blood pressure medicine, social support and stress management). The coach may also offer topics to the participant based upon barriers or concerns discussed during the call. A module is a "topic" to discuss which includes a coach's education/counseling, associated handouts, and references (see module overview in table below). The participant may focus on the same topics throughout the intervention based upon their personal needs or change the topics with every call. Home blood pressure monitoring will be discussed during each call by the health coach.

MyHEART Health Coach Educational Modules	
Module	Topics
Home Blood Pressure Monitoring	How to measure blood pressure, include members in household to avoid isolation, what do the numbers mean
Hypertension Knowledge	Define blood pressure, goal blood pressure, long-term health consequences
Low Sodium	Reading labels, effects of sodium on blood pressure, culturally appropriate cooking alternatives, eating with peers, meal planning, shopping on a budget
DASH Eating Plan	DASH components, meal planning, grocery shopping on a budget, DASH with peers; Cultural and personal food preferences; Discuss cultural meaning of dietary practices
Weight Loss/ Maintenance	Relationship of weight with hypertension, dietary and activity options to lose weight, time management, social support to assist with weight loss, fitness apps
Smoking Cessation*	Negative effects of tobacco on heart health, social/peer influence
Moderate Alcohol Consumption	Negative effects on heart health; define quantity for types of alcohol
Blood Pressure Medicine	Why medications may be needed, side effects, adherence, possible lifelong commitment, remembering medication, cost
Social Support	Local resources for support, reducing clinic no-shows, peer/social support
Stress Management	Identifying ways to reduce stress, stress with life's transitions and new challenges
*Only for active tobacco users	

The content of coach-participant interactions will focus on: 1) highlighting discrepancies between participants' current health behaviors and their desired behavior goals to promote internal motivation, 2) sharing reference points for guideline-recommended behaviors to lower blood pressure, and 3) discussing short-term goals and developing congruent action plans. Coaches will promote autonomy by individualizing the order and depth of educational content based on the behavioral goals chosen by the subject. Subjects will be coached on practical skill building (e.g., label reading) and coaches will encourage patients to set goals that are motivating but not overwhelming. The "Coach's Guide" is to build on the coach's knowledge of blood pressure lowering behavioral techniques and how to use the self-determination theory and motivational interviewing to guide the subject as they initiate and try to maintain their new health behaviors. Abbreviated guides in the appendix highlight important "talking points" for the coach to address during each call. Hypertension guidelines on exercise and dietary changes will be given to the participant by the health coach, based upon the updated guidelines available at the time. Coach references will be updated if new guidelines and scientific recommendations become available during this study.

All intervention participants will start with the home blood pressure monitoring module. The first follow-up phone call will address hypertension knowledge and review home blood pressure monitoring. Home blood pressure monitoring education will also be provided during all follow-up phone calls. The order of the remaining modules will be guided by participant's choice and tailored to their goals.^{170,171} Fewer modules than calls allows some topics to be repeated as

needed and per the participants' requests. Current tobacco users will be referred to the Wisconsin Tobacco Quit Line (<http://www.ctri.wisc.edu/quitline.html>) when ready to attempt cessation and their primary care provider will be notified of their intention to quit via the EHR. The participant will be encouraged to also discuss alcohol reduction/cessation with their primary care provider if they report consuming >14 alcohol beverages/week.¹²² The MyHEART team created handouts to include specific topics requested by our young adult focus groups (see Appendix). The MyHEART handouts were formatted with a Flesch-Kincaid readability of ≤6th grade.¹⁷²

5.4.3 Follow up:

Table. Acceptable Window for Study Visits (including weekends)

Visit	Window	Activities
Baseline (Visit 1)	No more than 30 days from telephone screening phone call	Written, informed consent, clinic blood pressure, 24-hour AMBP placement, provide participant remuneration
Baseline (Visit 2)	No sooner than 24 hours after Visit 1 and no more than 21 days after Visit 1	Clinic blood pressure, 24-hour AMBP removal, if eligible, enrollment, randomization, baseline screening questions and assessment, provide participant remuneration
6-month (Visit 3)	No later than 30 days since the last health coach call (intervention arm) or the scheduler call (routine/usual care)	Clinic blood pressure, 24-hour AMBP placement, 6-month follow-up assessment (ex: BMI), questionnaires, provide participant remuneration
6-month (Visit 4)	No sooner than 24 hours from Visit 3 and no more than 21 days from Visit 3	24-hour AMBP removal, provide participant remuneration
12-month (Visit 5)	No later than 30 days since scheduler call (both intervention and usual care arm)	Clinic blood pressure, 24-hour AMBP placement, 6-month follow-up assessment (ex: BMI), questionnaires, provide participant remuneration
12-month (Visit 6)	No sooner than 24 hours from Visit 5 and no more than 21 days from Visit 5	24-hour AMBP removal, provide participant remuneration

5.4.4 Unscheduled:

- Unscheduled visits are not included in this study.
- See the appendix for the study calendar with procedures and data collection
- Participants will be encouraged to continue routine blood pressure follow-up with their primary and routine healthcare team. Otherwise, no additional concomitant therapies be advised or suggested.

